**1. Definitions of image-related events**

At each follow-up imaging visit (each value of FIMG:CPEVENT), each patient is classified as follows:

endoleak, any

yes if	on follow-up fenestrated imaging form, endoleak = yes (FIMG:ENDOYN = "YES")
no if	on follow-up fenestrated imaging form, endoleak = no (FIMG:ENDOYN = "NO")
missing otherwise	

endoleak, type I

yes if	on follow-up fenestrated imaging form, type I is checked (FIMG:ENDTYP1 = 1)
no if	on follow-up fenestrated imaging form, endoleak has been answered (FIMG:ENDOYN = "YES" or FIMG:ENDOYN = "NO") AND
	on follow-up fenestrated imaging form, type I is not checked (FIMG:ENDTYP1 = NULL)
missing otherwise	

endoleak, type II

yes if	on follow-up fenestrated imaging form, type II is checked (FIMG:ENDTYP2 = 1)
no if	on follow-up fenestrated imaging form, endoleak has been answered (FIMG:ENDOYN = "YES" or FIMG:ENDOYN = "NO") AND
	on follow-up fenestrated imaging form, type II is not checked (FIMG:ENDTYP2 = NULL)
missing otherwise	

endoleak, type III

yes if	on follow-up fenestrated imaging form, type III is checked (FIMG:ENDTYP3 = 1)
no if	on follow-up fenestrated imaging form, endoleak has been answered (FIMG:ENDOYN = "YES" or FIMG:ENDOYN = "NO") AND
	on follow-up fenestrated imaging form, type III is not checked (FIMG:ENDTYP3 = NULL)
missing otherwise	

endoleak, type IV

yes if	on follow-up fenestrated imaging form, type IV is checked (FIMG:ENDTYP4 = 1)
no if	on follow-up fenestrated imaging form, endoleak has been answered (FIMG:ENDOYN = "YES" or FIMG:ENDOYN = "NO") AND
	on follow-up fenestrated imaging form, type IV is not checked (FIMG:ENDTYP4 = NULL)
missing otherwise	

endoleak, unknown

yes if	on follow-up fenestrated imaging form, unknown is checked (FIMG:ENDTYP5 = 1)
no if	on follow-up fenestrated imaging form, endoleak has been answered (FIMG:ENDOYN = "YES" or FIMG:ENDOYN = "NO") AND
	on follow-up fenestrated imaging form, unknown is not checked (FIMG:ENDTYP5 = NULL)
missing otherwise	

growth notation:

- A1\_p = maximum aneurysm diameter major axis on follow-up fenestrated imaging form (FIMG:DIAMEA1) at pre-discharge visit

- A1\_c = maximum aneurysm diameter major axis on follow-up fenestrated imaging form (FIMG:DIAMEA1) at current visit
- A2\_p = maximum aneurysm diameter minor axis on follow-up fenestrated imaging form (FIMG:DIAMEA2) at pre-discharge visit
- A2\_c = maximum aneurysm diameter minor axis on follow-up fenestrated imaging form (FIMG:DIAMEA2) at current visit

aneurysm growth (only defined for visits after pre-discharge [FIMG:CPEVENT = "PRE\_DISCHARGE"])

yes if	A1_c – A1_p > 5 OR
	A2_c – A2_p > 5
no if	A1_c – A1_p ≤ 5 AND
	A2_c – A2_p ≤ 5
missing otherwise	

aneurysm shrinkage (only defined for visits after pre-discharge [FIMG:CPEVENT = "PRE\_DISCHARGE"])

yes if	A1_c – A1_p < -5 OR
	A2_c – A2_p < -5
no if	A1_c – A1_p ≥ -5 AND
	A2_c – A2_p ≥ -5
missing otherwise	

aneurysm stasis (only defined for visits after pre-discharge [FIMG:CPEVENT = "PRE\_DISCHARGE"])

yes if	aneurysm growth = no AND
	aneurysm shrinkage = no
no if	aneurysm growth = yes OR
	aneurysm shrinkage = yes
missing otherwise	

migration notation:

- M4\_p = table position of uppermost proximal stent on follow-up fenestrated imaging form (FIMG:MIGTP4) at pre-discharge visit
- M4\_c = table position of uppermost proximal stent on follow-up fenestrated imaging form (FIMG: MIGTP4) at current visit
- M5\_p = table position of initial appearance of full circumference of stent on follow-up fenestrated imaging form (FIMG: MIGTP5) at pre-discharge visit
- M5\_c = table position of initial appearance of full circumference of stent on follow-up fenestrated imaging form (FIMG: MIGTP5) at current visit
- M1\_p = table position of SMA on follow-up fenestrated imaging form (FIMG: MIGTP1) at pre-discharge visit

- M1\_c = table position of SMA on follow-up fenestrated imaging form (FIMG: MIGTP1) at current visit

migration (only defined for visits after pre-discharge [FIMG:CPEVENT = "PRE\_DISCHARGE"])

yes if	$ (M1\_c - M4\_c) - (M1\_p - M4\_p)  > 10$ OR
	$ (M1\_c - M5\_c) - (M1\_p - M5\_p)  > 10$
no if	$ (M1\_c - M4\_c) - (M1\_p - M4\_p)  \leq 10$ AND
	$ (M1\_c - M5\_c) - (M1\_p - M5\_p)  \leq 10$
missing otherwise	

stent fracture

yes if	on follow-up fenestrated KUB form, proximal graft stent fracture = "YES" (FKUB:DISF1 = "YES") OR
	on follow-up fenestrated KUB form, distal graft stent fracture = "YES" (FKUB:DISF2 = "YES") OR
	on follow-up fenestrated KUB form, right iliac stent fracture = "YES" (FKUB:DISF3 = "YES") OR
	on follow-up fenestrated KUB form, left iliac stent fracture = "YES" (FKUB:DISF4 = "YES") OR
	on follow-up fenestrated KUB form, occluder stent fracture = "YES" (FKUB:DISF5 = "YES") OR
	on follow-up fenestrated KUB form, converter stent fracture = "YES" (FKUB:DISF6 = "YES") OR
	on follow-up fenestrated KUB form, right iliac leg extension stent fracture = "YES" (FKUB:DISF7 = "YES") OR
	on follow-up fenestrated KUB form, left iliac leg extension stent fracture = "YES" (FKUB:DISF8 = "YES") OR
	on follow-up fenestrated KUB form, main body extension stent fracture = "YES" (FKUB:DISF9 = "YES") OR
	on follow-up fenestrated KUB form, renal stent right stent fracture = "YES" (FKUB:DISF10 = "YES") OR
	on follow-up fenestrated KUB form, renal

	stent left stent fracture = "YES" (FKUB:DISF11 = "YES") OR
	on follow-up fenestrated KUB form, other stent fracture = "YES" (FKUB:DISF12 = "YES")
no if	on follow-up fenestrated KUB form, proximal graft stent fracture = "NO" or "N/A" (FKUB:DISF1 = "NO" or "N/A") AND
	on follow-up fenestrated KUB form, distal graft stent fracture = "NO" or "N/A" (FKUB:DISF2 = "NO" or "N/A") AND
	on follow-up fenestrated KUB form, right iliac stent fracture = "NO" or "N/A" (FKUB:DISF3 = "NO" or "N/A") AND
	on follow-up fenestrated KUB form, left iliac stent fracture = "NO" or "N/A" (FKUB:DISF4 = "NO" or "N/A") AND
	on follow-up fenestrated KUB form, occluder stent fracture = "NO" or "N/A" (FKUB:DISF5 = "NO" or "N/A") AND
	on follow-up fenestrated KUB form, converter stent fracture = "NO" or "N/A" (FKUB:DISF6 = "NO" or "N/A") AND
	on follow-up fenestrated KUB form, right iliac leg extension stent fracture = "NO" or "N/A" (FKUB:DISF7 = "NO" or "N/A") AND
	on follow-up fenestrated KUB form, left iliac leg extension stent fracture = "NO" or "N/A" (FKUB:DISF8 = "NO" or "N/A") AND
	on follow-up fenestrated KUB form, main body extension stent fracture = "NO" or "N/A" (FKUB:DISF9 = "NO" or "N/A") AND
	on follow-up fenestrated KUB form, renal stent right stent fracture = "NO" or "N/A" (FKUB:DISF10 = "NO" or "N/A") AND
	on follow-up fenestrated KUB form, renal stent left stent fracture = "NO" or "N/A" (FKUB:DISF11 = "NO" or "N/A") AND
	on follow-up fenestrated KUB form, other stent fracture = "NO" or "N/A" (FKUB:DISF12 = "NO" or "N/A")
missing otherwise	

barb fracture

yes if	on follow-up fenestrated KUB form, barb bend is checked (FKUB:PFSNIN1 = 1) OR
	on follow-up fenestrated KUB form, proximal stent separation is checked (FKUB:PFSNIN3 = 1) OR
	on follow-up fenestrated KUB form, barb separation is checked (FKUB:PFSNIN2 = 1)
no if	on follow-up fenestrated KUB form, barb bend is not checked (FKUB:PFSNIN1 = NULL) AND
	on follow-up fenestrated KUB form, proximal stent separation is not checked (FKUB:PFSNIN3 = NULL) AND
	on follow-up fenestrated KUB form, barb separation is not checked (FKUB:PFSNIN2 = NULL)
missing otherwise	

component separation

yes if	on follow-up fenestrated KUB form, "Has component separation of the endovascular graft occurred?" = "YES" (FKUB:COMSYN = "YES")
no if	on follow-up fenestrated KUB form, "Has component separation of the endovascular graft occurred?" = "NO" (FKUB:COMSYN = "NO")
missing otherwise	

compression

yes if	on follow-up fenestrated KUB form, renal stent right compression = "YES" (FKUB:DEVCPR1 = "YES") OR
	on follow-up fenestrated KUB form, renal stent left compression = "YES" (FKUB:DEVCPR2 = "YES") OR
	on follow-up fenestrated KUB form, other stent compression = "YES" (FKUB:DEVCPR3 = "YES")
no if	on follow-up fenestrated KUB form, renal

	stent right compression = "NO" or "N/A" (FKUB:DEVCPR1 = "NO" or "N/A") AND
	on follow-up fenestrated KUB form, renal stent left compression = "NO" or "N/A" (FKUB:DEVCPR2 = "NO" or "N/A") AND
	on follow-up fenestrated KUB form, other stent compression = "NO" or "N/A" (FKUB:DEVCPR3 = "NO" or "N/A")
missing otherwise	

occlusion, right iliac artery CIA

yes if	on follow-up fenestrated imaging form, right iliac artery patent CIA = "YES" (FIMG:PATCIA1 = "NO")
no if	on follow-up fenestrated imaging form, right iliac artery patent CIA = "YES" (FIMG:PATCIA1 = "YES")
missing otherwise	

occlusion, right iliac artery IIA

yes if	on follow-up fenestrated imaging form, right iliac artery patent IIA = "YES" (FIMG:PATIIA1 = "NO")
no if	on follow-up fenestrated imaging form, right iliac artery patent IIA = "YES" (FIMG:PATIIA1 = "YES")
missing otherwise	

occlusion, left iliac artery CIA

yes if	on follow-up fenestrated imaging form, left iliac artery patent CIA = "YES" (FIMG:PATCIA2 = "NO")
no if	on follow-up fenestrated imaging form, left iliac artery patent CIA = "YES" (FIMG:PATCIA2 = "YES")
missing otherwise	

occlusion, left iliac artery IIA

yes if	on follow-up fenestrated imaging form, left iliac artery patent IIA = "YES"
--------	--

	(FIMG:PATIIA2 = "NO")
no if	on follow-up fenestrated imaging form, left iliac artery patent IIA = "YES" (FIMG:PATIIA2 = "YES")
missing otherwise	

occlusion, right renal

yes if	on follow-up fenestrated imaging form, right renal occluded is checked (FIMG:PATRRA = "OCCLUDED")
no if	on follow-up fenestrated imaging form, right renal patent is checked (FIMG:PATRRA = "PATENT")
missing otherwise	

occlusion, left renal

yes if	on follow-up fenestrated imaging form, left renal occluded is checked (FIMG:PATLRA = "OCCLUDED")
no if	on follow-up fenestrated imaging form, left renal patent is checked (FIMG:PATLRA = "PATENT")
missing otherwise	

occlusion, SMA

yes if	on follow-up fenestrated imaging form, SMA occluded is checked (FIMG:PATSMA = "OCCLUDED")
no if	on follow-up fenestrated imaging form, SMA patent is checked (FIMG:PATSMA = "PATENT")
missing otherwise	

occlusion, celiac

yes if	on follow-up fenestrated imaging form, celiac occluded is checked (FIMG:PATCEL = "OCCLUDED")
no if	on follow-up fenestrated imaging form, celiac patent is checked (FIMG:PATCEL = "PATENT")
missing otherwise	

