### 3. Summary reports for events

At selected visits, the following is reported for each event:

1. number of subjects with event = yes
2. (number of subjects with event = yes) + (number of subjects with event = no)

The selected visits are as follows:

- pre-discharge (FIMG/FUP:CPEVENT = "PRE\_DISCHARGE")
- 1 month (FIMG/FUP:CPEVENT = "1 MONTH FUP")
- 6 months (FIMG/FUP:CPEVENT = "6 MONTH FUP")
- 12 months (FIMG/FUP:CPEVENT = "12 MONTH FUP")
- 24 months (FIMG/FUP:CPEVENT = "24 MONTH FUP")
- 36 months (FIMG/FUP:CPEVENT = "3 YEAR FUP")
- 48 months (FIMG/FUP:CPEVENT = "4 YEAR FUP")
- other (FIMG/FUP:CPEVENT = "OTHER")

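### An endoleak recorded with no type ticked falls into no type row, not even 'unknown', so on consistent forms the type I and III counts are minimum values

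*SAP*

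**What the plan says.** SAP section 1 classifies each imaging visit from one yes/no field (ENDOYN) and five tick boxes (ENDTYP1 to ENDTYP4 for types I to IV, ENDTYP5 for unknown).

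- Any endoleak is 'yes' on "on follow-up fenestrated imaging form, endoleak = yes (FIMG:ENDOYN = 'YES", whatever the type boxes show.
- Type I is 'yes' on "on follow-up fenestrated imaging form, type I is checked (FIMG:ENDTYP1 = 1".
- Type I is 'no' when two conditions hold. The first is "endoleak has been answered (FIMG:ENDOYN = 'YES' or FIMG:ENDOYN = 'NO') AND", which a visit with an endoleak also satisfies. The second is "on follow-up fenestrated imaging form, type I is not checked (FIMG:ENDTYP1 = NULL". Types II to IV have the same structure; for type III the second condition is "on follow-up fenestrated imaging form, type III is not checked (FIMG:ENDTYP3 = NULL".
- Unknown is 'yes' on "on follow-up fenestrated imaging form, unknown is checked (FIMG:ENDTYP5 = 1". It is 'no' when the endoleak question was answered and "on follow-up fenestrated imaging form, unknown is not checked (FIMG:ENDTYP5 = NULL" holds.

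None of these type rules looks at any other type box. Section 3 reports, per event and visit, the number 'yes' and the sum "number of subjects with event = yes) + (number of subjects with event = no". Section 7.2 lays these out as two rows per event. Section 7.3 adds a separate patient-level report for each event.

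**The concern.** An answered ENDOYN shows that the presence of a leak was assessed. It does not show that the type was determined. The rules nevertheless turn a blank type box into a definite 'no' in two situations where the type is unresolved: when 'unknown' is ticked, and when an endoleak is recorded with nothing ticked.

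The second situation contradicts itself. The visit has an endoleak, yet it is negative for every category, including the one meant for leaks of undetermined type. The 'unknown' row then understates the number of such leaks.

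In both situations the visit enters the type I and type III denominators as a non-event. Someone who divides the two printed counts obtains a figure that ignores the unresolved leaks, and the summary table does not say how many there are in all.

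Elsewhere the same section is stricter. Stent fracture and compression are 'no' only if every component carries an explicit NO or N/A; a blank component with no YES elsewhere gives 'missing'.

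**Working it through.** The SAP states no rate or count for this point, so there is no figure to reproduce. The check has two parts.

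**Part 1: apply the section 1 rules to the possible forms.**

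| ENDOYN | Boxes ticked | Any | I | II | III | IV | Unknown |
|---|---|---|---|---|---|---|---|
| YES | none | yes | no | no | no | no | no |
| YES | unknown only | yes | no | no | no | no | yes |
| YES | II and unknown | yes | no | yes | no | no | yes |
| YES | I only | yes | yes | no | no | no | no |
| NO | none | no | no | no | no | no | no |
| NO | I only | no | yes | no | no | no | no |
| blank | none | missing | missing | missing | missing | missing | missing |
| blank | I only | missing | yes | missing | missing | missing | missing |

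Row 1 is the contradiction. Row 2 is the leak of stated unknown type, visible in its own row. The sixth and eighth rows are conflicting forms: a type is counted 'yes' while any endoleak is 'no' or 'missing'.

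*Can row 1 be recovered from the summary table?* Not in general, because one form may carry several ticks. Take two visits with leaks:

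- One form has I and II ticked and the other has nothing ticked: any = 2, I = 1, II = 1, all other types 0.
- One form has I ticked and the other has II ticked: any = 2, I = 1, II = 1, all other types 0.

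The summary rows are identical, although the first pair contains an untyped leak.

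**Part 2: how far the implied proportion could move.** All counts here are assumed, for illustration only: N = 100 forms with ENDOYN answered, 20 with an endoleak, x = 3 with type I ticked, and u leaks of unresolved type without a type I tick. The formulas are:

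- table as planned: x/N
- upper bound, if every unresolved leak were type I: (x + u)/N
- if unresolved leaks had the type mix of the resolved ones: (x + x·u/(20 − u))/N
- if unresolved leaks were set to missing: x/(N − u)

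| u | As planned | Upper bound | Same mix | Set to missing |
|---|---|---|---|---|
| 2 | 3/100 = 3.0% | 5/100 = 5.0% | (3 + 6/18)/100 = 3.3% | 3/98 = 3.1% |
| 5 | 3/100 = 3.0% | 8/100 = 8.0% | (3 + 15/15)/100 = 4.0% | 3/95 = 3.2% |
| 8 | 3/100 = 3.0% | 11/100 = 11.0% | (3 + 24/12)/100 = 5.0% | 3/92 = 3.3% |

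The planned figure does not respond to u at all. Setting unresolved leaks to missing hardly moves it and stays below the same-mix value, because it removes only visits with a leak from the denominator. It also spoils the range: for u = 5 the printed denominator becomes 95, and a reader would form 3/95 = 3.2% to 8/95 = 8.4% instead of 3.0% to 8.0%.

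**The case against.** The strongest reply is that much of this is already disclosed. 'Endoleak, unknown' is a separate event printed at every visit, and on consistent forms all six endoleak rows share one denominator. A reader can already form type I over N, and type I plus unknown over N. That stands for leaks ticked as unknown, except that a form with both type I and unknown ticked would be counted twice. It does not help with leaks that have no box ticked.

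Second, the patient-level reports in section 7.3 would show any = 1 with all five types = 0. A reader might infer that these leaks are lost; they are not. They can be found by joining six separate reports, but not read from the summary table alone.

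Third, a reader might infer that the type I and III figures can only be too low. The SAP does not support that without qualification. A type tick counts as 'yes' even when ENDOYN is NO or blank, and a form with ENDOYN blank enters the type I row only if type I is ticked, which pushes the proportion up. The minimum-value statement therefore needs internally consistent forms.

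Fourth, the capture screens may force a type tick whenever an endoleak is recorded. The SAP states no such check. If one exists, the case with no box ticked cannot arise and only the ticked-unknown case remains. The validation in section 6 would not reveal the problem, since it compares derived data with the capture screens and a correctly programmed rule would pass.

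Finally, the SAP prints two counts per event, with no percentage, interval or test for endoleak type. That is correct, and it limits the weight of the point.

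**Conclusion.** The point holds as a minor one. The rules in section 1 return a self-contradictory result for an endoleak with no type ticked, and the 'unknown' row understates leaks of undetermined type by the number of such forms. On forms where ENDOYN and the type boxes agree, the type I and III proportions implied by the printed counts are minimum values.

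The size cannot be stated from the SAP, because it gives no number of untyped leaks. The 5%, 8% and 11% upper bounds rest on assumed counts and on treating every unresolved leak as type I; they show the mechanism and are not an estimate.

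A reader might go further and infer that the plan hides all leaks of undetermined type, or that recoding them to missing would correct the figures. Neither follows: leaks ticked as unknown have their own row, and recoding to missing leaves the proportion almost unchanged and makes the range harder to read.

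**What to change.** 1. Define 'endoleak, unknown' as 'yes' if ENDTYP5 = 1, or if ENDOYN = YES and ENDTYP1 to ENDTYP5 are all NULL. Define it as 'no' only if ENDTYP5 is NULL and either ENDOYN = NO, or ENDOYN = YES with at least one of types I to IV ticked.
2. Keep the common denominator (ENDOYN answered) for all type rows. Do not recode unresolved leaks to missing.
3. Beside the type I and type III rows, print the number of unresolved leaks not already ticked as that type. The range from yes/N to (yes + unresolved)/N can then be read directly, without double counting.
4. Query forms with a type ticked where ENDOYN is not YES.

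The change uses fields already collected. It costs one reworded definition, one extra count beside each of the two rows, the queries, and a slightly larger 'unknown' row.

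### Sac growth and shrinkage can both be 'yes' for one subject, and a record with one axis missing can count only as a change, which raises growth and shrinkage, lowers stasis and can split the denominators

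*SAP*

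**What the plan says.** SAP section 1 compares each follow-up diameter with the pre-discharge value, separately for the major axis (A1) and the minor axis (A2, for example "maximum aneurysm diameter minor axis on follow-up fenestrated imaging form (FIMG:DIAMEA2) at current visit"). Three events are derived from the two differences:

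- **Growth**, headed "aneurysm growth (only defined for visits after pre-discharge": yes if either axis rises by more than 5; no only if neither axis does, so both must be known.
- **Shrinkage**, headed "aneurysm shrinkage (only defined for visits after pre-discharge": yes if either axis falls by more than 5; no only if neither axis does.
- **Stasis**, headed "aneurysm stasis (only defined for visits after pre-discharge": the yes rule begins "aneurysm growth = no AND" and also needs shrinkage to be no. The no rule begins "aneurysm growth = yes OR" and is equally met by shrinkage being yes.

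Each definition ends with "missing otherwise". No rule covers axes that disagree or a record with only one usable axis. Section 3 builds the denominator event by event, as "number of subjects with event = yes) + (number of subjects with event = no", and section 7.2 prints all events in one report with a numerator row and a denominator row each.

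**The concern.** A reader will take growth, shrinkage and stasis at a visit as three descriptions of the same sacs. As written they need not be exclusive, and they need not rest on the same subjects.

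The more important problem is how incomplete records get in. The yes rule can be met with one axis and the no rule needs two, so a half-measured record is admitted or excluded according to its outcome. For growth this can be defended as cautious, since no observed enlargement is lost. For shrinkage the same rule works in the favourable direction: it raises the shrinkage rate, and it lets a sac with one axis up by more than 5 still count as shrunken.

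Missingness can also persist. Every comparison uses the pre-discharge value, so an axis not recorded then leaves all of that subject's later visits one-sided.

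**Working it through.** The SAP states no figure for this point, so there is none to reproduce. The check applies the rules in section 1 and the denominator in section 3.

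**Step 1: truth table.** Let d1 and d2 be the changes in major and minor axis from pre-discharge. A missing axis makes its comparison unknown, which is the natural reading of the residual category.

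| d1 | d2 | growth | shrinkage | stasis |
|---|---|---|---|---|
| +8 | +8 | yes | no | no |
| −8 | −8 | no | yes | no |
| 0 | 0 | no | no | yes |
| +8 | −8 | **yes** | **yes** | no |
| +8 | missing | yes | missing | no |
| −8 | missing | missing | yes | no |
| +5, 0 or −5 | missing | missing | missing | missing |

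The table is the same with the axes exchanged. A half-measured record is never growth = no, shrinkage = no or stasis = yes.

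**Step 2: denominators.** Take C complete records, g half-measured records with the known axis above +5, and s with it below −5. Yes plus no then gives:

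- growth: C + g
- shrinkage: C + s
- stasis: C + g + s

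If g = s = 0, all three equal C.

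**Step 3: illustration with assumed counts.** Take 90 complete records (10 growth, 39 shrinkage, 1 discordant, 40 stable) and 10 half-measured records (1 above +5, 4 below −5, 5 within ±5).

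| event | SAP rule | complete records only, same yes rules |
|---|---|---|
| growth | (10+1+1)/(90+1) = 12/91 = 13.2% | 11/90 = 12.2% |
| shrinkage | (39+1+4)/(90+4) = 44/94 = 46.8% | 40/90 = 44.4% |
| stasis | 40/(90+1+4) = 40/95 = 42.1% | 40/90 = 44.4% |

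The yes counts under the SAP rule sum to 12 + 44 + 40 = 96, over three different denominators.

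**Step 4: size of the bias over a range of missingness.** Let p be the either-axis rate with both axes recorded, q the rate seen on one axis alone, and m the share of records with one axis missing, unrelated to outcome. Then

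reported rate = [(1−m)p + mq] / [(1−m) + mq].

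For stasis, with true rate t and a share b of half-measured records beyond ±5,

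reported stasis = (1−m)t / [(1−m) + mb].

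All inputs are assumed: growth p = 10%, q = 8%; shrinkage p = 40%, q = 35%; stasis t = 50%, b = 8% + 35% = 43%.

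| m | growth (true 10%) | shrinkage (true 40%) | stasis (true 50%) |
|---|---|---|---|
| 1% | 10.1% | 40.2% | 49.8% |
| 2% | 10.1% | 40.4% | 49.6% |
| 5% | 10.4% | 41.1% | 48.9% |
| 10% | 10.8% | 42.2% | 47.7% |
| 20% | 11.8% | 44.8% | 45.1% |
| 30% | 13.0% | 47.8% | 42.2% |

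For example, growth at m = 5% is (0.95×0.10 + 0.05×0.08)/(0.95 + 0.05×0.08) = 0.099/0.954 = 10.4%.

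**Step 5: overlap.** Suppose measured changes were pure error, normal with mean 0, and independent between axes. The chance of opposite moves beyond 5 is 2×P(change > 5)². With SD 3 this is 2×0.048² = 0.5%; with SD 4 it is 2×0.106² = 2.2%. Real axes of one sac should move together. The growth inputs in step 4 imply that both axes exceed 5 in 8% + 8% − 10% = 6% of records, a correlation near 0.94 under a bivariate normal, and overlap is then essentially zero. The independent-axis figures therefore belong to a different scenario and should not be combined with step 4: independent axes at 8% each would give 1 − 0.92² = 15.4% growth, not 10%.

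**The case against.** Five arguments can be made for leaving the text alone.

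1. **Both axes sit on the same imaging form, so one without the other may be uncommon.** This stands as a limit on size. At 1–2% half-measured, growth moves by about 0.1 percentage points. A reader might infer that the three rows will always have different denominators, or that the trial's growth rate is materially inflated. The SAP supports neither: denominators differ only if an axis is missing and the other moved beyond 5, and no missingness figure is given.

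2. **Opposite moves beyond 5 are close to theoretical.** Largely right. A reader might infer that double counting is common; step 5 suggests it is rare. The rule still gives no answer when it happens.

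3. **Positive if any component is positive, negative only if all are negative, is the SAP's usual pattern.** It also governs migration, stent fracture and compression, and it preserves an observed positive. That is a fair reason not to discard such records, and the fix lists them. It does not justify putting them in a proportion from which the matching negatives are excluded. Nor is the pattern universal: the creatinine rule in section 2 works the other way, so a half-measured record there can enter only as no.

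4. **Denominators are printed, and the patient-level reports in section 7.3 show each 0, 1 or missing.** The SAP never says that the three rows partition the sample. True, so the cases can be traced. Printing a denominator selected on outcome does not remove the bias.

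5. **Giving growth precedence over shrinkage is a choice that nothing in the SAP dictates.** True. Some stated rule is needed for exclusive classes, and this one does not let a sac with a growing axis count as shrunken.

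**Conclusion.** The definitions allow one subject to be both growth and shrinkage at the same visit, and they admit half-measured records to growth and shrinkage only as yes and to stasis only as no. This follows from the stated rules and is not a detail left open. The direction of bias (growth and shrinkage up, stasis down) assumes that a missing axis is unrelated to how the sac behaved and makes its comparison unknown.

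The size depends on a missingness share that the SAP does not give. On the assumed inputs it is negligible at 1–2% and reaches about 3 percentage points for growth, and nearly 8 for shrinkage and stasis, at 30%. With complete pairs the bias is zero and only the rare overlap is left. The SAP attaches no test or threshold to these rows, so the priority is low to moderate.

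**What to change.** In SAP section 1:

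- For the reported proportions, set growth, shrinkage and stasis all to missing unless both axis differences are available.
- Count shrinkage as yes only where growth is no. The three classes are then exclusive and share one denominator. In the step 3 illustration this gives 11 + 39 + 40 = 90 of 90.
- Beside the table, list every half-measured record whose known axis changed by more than 5 in either direction, so that no observed growth is hidden.
- Apply the same complete-record denominator to migration, whose either-measure yes rule and both-measures no rule have the same one-sided structure.

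The cost is a few words in these definitions, a small code change and one listing. The downside is that half-measured positives move from the rate to the listing. Stent fracture and compression would keep the any-positive convention, so the SAP should say in one sentence that the difference is deliberate.

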## 7.2. Events: Summary report

All events will be included in a single report, which will have one column for each visit and two rows for each event, as follows:

event		pre-discharge	visit 1-month	(etc.)
endoleak, any	number yes	#	#	
	number yes or no	#	#	
endoleak, type I	number yes	#	#	
	number yes or no	#	#	
(etc.)				

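### The event named barb fracture pools barb bend, barb separation and proximal stent separation, so its name is not true of every case counted and proximal stent separation cannot be identified in any planned report

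*SAP*

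**What the plan says.** SAP section 1 sets the event *barb fracture* to yes on any one of three ticked boxes. One is PFSNIN1, for a bent barb. Another is PFSNIN2, for a barb that has separated. The remaining one does not refer to a barb: "on follow-up fenestrated KUB form, proximal stent separation is checked (FKUB:PFSNIN3 = 1) OR".

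The event is no when all three boxes are empty, for example "on follow-up fenestrated KUB form, proximal stent separation is not checked (FKUB:PFSNIN3 = NULL) AND".

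Two neighbouring events in the same section might be expected to hold a stent separation, but they draw on other fields. *Stent fracture* uses DISF1 to DISF12, beginning with "on follow-up fenestrated KUB form, proximal graft stent fracture". *Component separation* uses COMSYN alone, which records the answer to "Has component separation of the endovascular graft occurred".

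For reporting, section 7.2 states: "All events will be included in a single report, which will have one column for each visit and two rows for each event". The two rows are the number with yes and the number with yes or no. Section 7.3 gives one value (0, 1 or missing) per event, subject and visit.

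**The concern.** The form gives each of the three findings its own box, and the SAP merges them under a name that does not describe them all. On the form's own terms a bend is recorded apart from a separation, and the third box concerns the proximal stent and not a barb. A reader of the summary table sees only the words barb fracture and a count.

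Two things are at stake. First, the count cannot be read as its name suggests. Second, proximal stent separation, a device-integrity finding that was judged worth its own box, cannot be picked out of any planned table or listing.

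**Working it through.** The SAP states no rate or count for this event, so there is no figure to reproduce. The check is of the rule itself, followed by an illustration.

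**Step 1. All box patterns under the section 1 rule.** Each box is ticked (1) or empty (–), which gives 2 × 2 × 2 = 8 patterns.

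| Bend (PFSNIN1) | Barb separation (PFSNIN2) | Proximal stent separation (PFSNIN3) | Event as defined |
|---|---|---|---|
| – | – | – | no |
| 1 | – | – | yes |
| – | – | 1 | yes |
| 1 | – | 1 | yes |
| – | 1 | – | yes |
| 1 | 1 | – | yes |
| – | 1 | 1 | yes |
| 1 | 1 | 1 | yes |

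Seven of the 8 patterns give yes. Four of the seven include barb separation and three do not. One of those three, proximal stent separation alone, has neither barb box ticked.

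**Step 2. Where else PFSNIN3 is used.** Among the events in sections 1 and 2, stent fracture uses DISF1–12, component separation uses COMSYN and compression uses DEVCPR1–3. The remaining events use imaging-form or creatinine fields. PFSNIN3 appears only under barb fracture. A form with PFSNIN3 ticked, COMSYN = NO and every DISF field NO or N/A would be reported as barb fracture yes, component separation no and stent fracture no. The rules allow that combination; the SAP does not show whether it occurs.

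**Step 3. What the count can be.** It follows from step 1 that

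number yes = number with barb separation + number with a bend or stent separation but no barb separation.

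The second term is zero or positive, so the count is never below the number with barb separation.

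**Step 4. Illustration with assumed rates** (none comes from the SAP). Take barb separation 1% and proximal stent separation 0.5% among forms that were read. The combined rate lies between the largest single rate (full overlap) and the sum (no overlap).

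| Assumed bend rate | Full overlap | Independent findings | No overlap | Excess over the 1% with barb separation |
|---|---|---|---|---|
| 1% | 1.0% | 1 − 0.99 × 0.99 × 0.995 = 2.48% | 1 + 1 + 0.5 = 2.5% | 0 to 1.5 points |
| 3% | 3.0% | 1 − 0.97 × 0.99 × 0.995 = 4.45% | 3 + 1 + 0.5 = 4.5% | 2.0 to 3.5 points |

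Across both rows the excess runs from 0 to 3.5 points. In general it cannot exceed the bend rate plus the stent separation rate.

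**Step 5. The denominator.** The rule for no accepts empty boxes without requiring that the form was answered, so every pattern in step 1 is yes or no and none is missing. If a share f of the forms counted were blank, the printed proportion would be (1 − f) times the rate among forms read. With the 2.5% above and an assumed f of 0.6, it would be 0.4 × 2.5% = 1.0%, the same as the barb separation rate among forms read. The direction in step 3 is therefore certain for the count but not for the proportion.

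**The case against.** The best defence is that the composite is open. All three components are listed with their field names in both the yes and the no rule, so anyone with the SAP can see what is counted. Pooling is also this SAP's habit: stent fracture pools twelve fields and compression pools three, each into one event. These are descriptive counts by visit, no test or decision rule in the SAP uses them, and the three fields stay in the database for later tabulation.

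Much of this stands, and it limits the consequence. It does not remove the point. Stent fracture and compression each pool one kind of finding across sites, under a name that is true of every member. Barb fracture pools different kinds of finding under a name that is not. A reader who looks up the definition still cannot recover the three counts from the planned reports.

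A reader might also infer more than the document supports:

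- *That barb separation is the true barb fracture and the rest is error.* The form has a box for barb separation; the SAP never equates the two terms, and the form and its instructions are not shown.
- *That the printed rate is overstated.* The excess in the count may be zero, and the proportion also depends on how blank forms are handled.
- *That one finding dominates the row.* Without rates this cannot be said.
- *That stent separation is lost.* It is counted under barb fracture. Some cases might also be entered under COMSYN, on which the SAP is silent, but that row would not identify them as proximal stent separations.

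**Conclusion.** The point holds as a fault of naming and reporting. The row combines three separately recorded findings, its name does not fit all of them, and proximal stent separation cannot be identified in any planned report. These conclusions follow from the definitions and the report layouts and need no assumed rate.

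The size of the effect is not known. The excess of the count over barb separation is at least zero; the range of 0 to about 3.5 percentage points rests wholly on the assumed rates in the illustration. The document does not support a claim that barb fracture is overstated by a given amount, or that its proportion is overstated at all. The consequence is confined to descriptive device-integrity tables, but the correction is cheap enough that it should be made.

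**What to change.** Replace the single event in section 1 by three events under their form names, each with its own two rows in the section 7.2 report and its own patient-level report under section 7.3:

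- barb bend: PFSNIN1 = 1
- barb separation: PFSNIN2 = 1
- proximal stent separation: PFSNIN3 = 1

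If a combined row is still wanted, keep it beside these and name it *any barb bend, barb separation or proximal stent separation*. Do not call PFSNIN2 a fracture unless the form defines it that way. The treatment of blank forms is a separate matter, but it affects the same definition and can be settled in the same edit.

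The cost is a change of SAP wording and a few extra descriptive rows, probably with small counts. All three fields are already collected.
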